6.3.2. Telephone Visit (Day 9 ±1)

The Investigator (or designee) will contact the parent(s)/guardian(s)/caregiver(s) by telephone on the third day of the fixed dose period to ensure study medication compliance and provide guidance for accurate dosing as required.

- Review compliance with dosing regimen.
- Review completion of dosing diary.
- Review concomitant medications and non-drug treatments and procedures, including any ongoing AED's.
- Assess and record adverse events.

6.3.3. Visit 5 Video-EEG (Day 12 to 14 ±1)

The following activities will be performed at Visit 5, which is scheduled to assess partial onset seizure frequency by inpatient Video-EEG monitoring.

- Placement of EEG electrodes and recording device and instruction of parent(s)/guardian(s)/caregiver(s) of its usage.
- Dispense seizure event log to track observed seizure events during Video-EEG and train parent(s)/guardian(s)/caregiver(s) on its use and completion.
- Record all concomitant medications and non-drug treatments and procedures, including any ongoing AED's.
- Evaluate and record study medication compliance.
- Collect and record vital signs.
- Assess and record adverse events.
- Collect and review dosing diary.
- Dispense daily dosing diary.

- Dosing compliance training/review and demonstration.

6.3.4. Visit 6 Begin Taper Phase (Day 15 ±2)

The Double-blind Fixed Dose Treatment phase is completed. Following completion of the 9-day fixed dose treatment and double-blind Video-EEG assessment subjects will begin the 1 week Taper Phase. Subjects who require early termination prior to Visit 6 should also begin the taper and follow the procedures for Visits 6 and 7 below.

- Collect blood and urine samples for clinical laboratory assessments. If it is not feasible to obtain a urine sample, then no urine sample will be required.
- CCI [REDACTED]
- CCI [REDACTED]
- Record all concomitant medications and non-drug treatments and procedures, including any ongoing AED's.
- Evaluate and record study medication compliance.
- Download on treatment Video-EEG recording data.
- Transmit Video-EEG data to central reader for assessment.
- Collect seizure event log and send to central reader.
- Assess and record adverse events.
- Collect and record vital signs, including BP and pulse.
- Collect and review dosing diary.
- Dispense study medication for taper.
- Dispense subject daily dosing diary.

6.4. Completion of Taper (End of Study/Early Termination)

The taper phase is completed at Visit 7. Subjects will complete Study A0081042 at this visit. Subjects may be screened for Study A0081106.

6.4.1. Visit 7 (Day 22 ±3)

- Record all concomitant medications and non-drug treatments and procedures, including any ongoing AED's.
- Perform 12-lead ECG.
- Perform full physical examination which includes recording vital signs including BP and pulse.
- Perform full neurological examination.
- Collect blood and urine specimens for clinical laboratory assessments. If it is not feasible to obtain a urine sample, then no urine sample will be required.
- Evaluate and record study medication compliance.
- Collect and review dosing diary.
- Assess and record adverse events.

If the subject terminates the study early, then samples for clinical laboratory analysis and CCI [REDACTED] will be collected at this visit. If greater than 48 hr have elapsed since the last dose of study medication, then do not collect CCI [REDACTED]:

- CCI [REDACTED]

6.5. Subject Withdrawal

Subjects may be withdrawn from the study at any time at their parent(s)/guardian(s) request, or they may be withdrawn at any time at the discretion of the investigator or sponsor for safety or behavioral reasons, or the inability of the subject/parent(s)/guardian(s) to comply with the protocol required schedule of study visits or procedures at a given site.

Events to consider that may result in withdrawal could include but are not limited to:

- Adverse events;
- Intercurrent illness;
- Loss to follow-up;
- Lack of efficacy;
- Exacerbation of seizures relative to screening/baseline;

- Non-compliance with study medication, protocol requirements, or study related procedures;
- Serious eligibility or violations of the protocol (eg, the subject does not have the target disease);
- Study termination by Sponsor or regulatory authorities;
- Parent's/guardian decision to withdraw/withdrawal of consent;
- Investigator discretion in case of occurrence of any medical condition, requirement for prohibited concomitant medication or treatment, or circumstances that would expose the subject to substantial risk and/or would not allow the subject to adhere to protocol requirements.

Protocol specified withdrawal procedures are the same as those to be performed at Visits 6 and 7 (Section [STUDY PROCEDURES](#)).

In certain instances subjects who require withdrawal from this study may still be eligible for screening for entry into long term safety Study A0081106. Such cases should be reviewed with the Pfizer study clinician to determine further eligibility. Subjects who are withdrawn due to reasons of loss to follow up, protocol non-compliance, protocol violations or who have withdrawn consent will not be eligible for Study A0081106 under any circumstances.

Under certain circumstances, when subjects leave the study early (early termination ET), dosing with the taper medication may be inadvisable. The decision not to taper the subject is upon agreement from the Sponsor's Study Clinician or Designee. If the taper will not be utilized then all assessments required at Visit 6 and 7 should be conducted as possible.

If a subject does not return for a scheduled visit, every effort should be made to contact the subject's parent/caregiver subject and information received during contact attempts must be documented in the subject's medical record). In any circumstance, every effort should be made to document subject outcome, if possible. The investigator should inquire about the reason for withdrawal, request that the parent(s)/guardian(s) return all unused investigational product, request that the subject/parent(s)/guardian(s) return for a final visit, if applicable, and follow-up with the parent(s)/guardian(s) regarding any unresolved adverse events.

If the subject withdraws from the trial and also withdraws consent for disclosure of future information, no further evaluations should be performed and no additional data should be collected. The sponsor may retain and continue to use any data collected before such withdrawal of consent.

7. ASSESSMENTS

Every effort should be made to ensure that the protocol required tests and procedures are completed as described. However it is anticipated that from time to time there may be circumstances, outside of the control of the investigator that may make it unfeasible to perform the test. In these cases the investigator will take all steps necessary to ensure the safety and well being of the subject. When a protocol required test cannot be performed the investigator will document the reason for this and any corrective and preventive actions which he/she has taken to ensure that normal processes are adhered to as soon as possible. The study sponsor will be informed of these incidents in a timely fashion.

7.1. Efficacy Assessments

Efficacy assessment will be evaluated based on seizure frequency in the last 48 hours of the 2 week double-blind treatment phase determined from the central read of the Video-EEG. The seizure event log will be utilized by the central reader to assist in evaluation of difficult to interpret Video-EEG findings. Assessment of efficacy is based on the reduction in the frequency of partial onset seizures during the same 48 hours of the 2 week double-blind treatment phase.

7.2. Acquisition of Seizure Counts: Video-Electroencephalogram (EEG)

Baseline and treatment phase Video-EEG will include a target minimum of 48 hours of continuous Video-EEG monitoring after placement of electrodes. Every reasonable attempt should be made to obtain the minimum target Video-EEG recording of 48 hours, which may require up to 72-hours of recording. Recognizing the inherent challenges in Video-EEG monitoring of pediatric subjects with epilepsy it is expected that the target minimum 48 hour Video-EEG recording may not be achievable in all cases. In the clinical investigator's opinion, should circumstances (eg, clinical care, child behavior, consent, etc.) mandate a Video-EEG monitoring period less than 48-hours for a given subject, please contact the study clinician to review the subject's clinical circumstances and document reasons for not achieving the target minimum Video-EEG duration. Results of the baseline monitoring must be available and reviewed by the central reader as soon as possible. EEG tracings will be done with a placement of 20 recording electrodes including FP1, FP2, F3, F4, C3, C4, P3, P4, O1, O2, F7, F8, T3, T4, T5, T6, Fz, Cz, Pz and reference and ground electrodes. The initial recording impedance should be below 5 KOhms.

7.2.1. Primary Efficacy Parameter

The primary efficacy parameter is the log transformed double blind 24-hour EEG seizure rate during Visit 6 (48-hour Video-EEG Assessment Phase) of the Double-Blind Treatment Phase.

This 24-hour seizure rate will be calculated for each subject using the following algorithm:

$$\text{Double Blind 24 - hr EEG seizure rate} = \frac{\text{\# of seizures in double blind 48 - hr assessment phase}}{\text{\# of hours of Video - EEG monitoring}} \times 24$$

A log-transformation will be applied to the 24-hr seizure rate for each subject after adding a value of " 1"; ie, \log_e (double blind 24-hr EEG seizure rate + 1). When the log-transformation is used, the quantity 1 is added to the double blind 24-hr EEG seizure rate for all subjects to account for any possible "0" seizure incidence. This will result in the following primary efficacy measure: \log_e (double blind 24-hr EEG seizure rate + 1). Results will be reported as "percent change in seizures" relative to placebo. For example, a difference between one of the pregabalin doses and placebo of -0.400 on the log transformed scale for the double blind 24-hr seizure rate, translates into a 33% reduction in the double blind 24-hour EEG seizure rate of the pregabalin group from the placebo group (ie, $100\% * [\exp^{-0.400} - 1] = -33\%$).

A minimum of 24 hours of evaluable Video-EEG will be required to utilize the data for analysis of efficacy. In cases where there is less than 24 hours of evaluable Video-EEG, the seizure rate will be set to missing.

The baseline 24-hr Video-EEG seizure rate will be calculated similarly.

7.2.2. Secondary Efficacy Parameter

A key secondary efficacy parameters is Responder Rate, defined as subjects who have a $\geq 50\%$ reduction from baseline in partial seizure rate during the double-blind 48 hour Video-EEG period. Subjects meeting this criterion will be considered responders.

7.3. Safety Assessments

All subjects who have taken 1 dose of study medication (Safety population) will be included in the evaluation for safety, using adverse event data (eg, occurrence, nature, intensity, and relationship to study drug and dosing level), clinical laboratory data, and the results of physical examinations, vital signs, neurological examinations and ECGs.

7.4. Clinical Laboratory Assessments

Blood and urine samples for clinical laboratory measurements will be analyzed by a central laboratory.

7.4.1. Estimated Creatinine Clearance (mL/min/1.73m²)

Creatinine clearance will be calculated by the central laboratory at Screening (Visit 1) only. For laboratories using the Jaffe chromogen reaction to quantify serum creatinine levels, the following equations should be used to calculate creatinine clearance. Other equations may be considered when serum creatinine levels are measured by other methods.

For Subjects ≥ 1 year of age and < 4 years of age:

$$Cl_{CR} = 0.55 \times \text{length (cm)} / \text{serum creatinine (mg/dL)}$$

For Subjects 1 month of age and < 1 year of age:

$$Cl_{CR} = 0.45 \times \text{length (cm)} / \text{serum creatinine (mg/dL)}$$

If the unit of the serum creatinine value is in micromoles/L, the serum creatinine concentration must first be converted to mg/dL using the following equation.

Converting serum creatinine concentration from μmoles/L to mg/dL:

$$\text{Serum Creatinine (mg/dL)} = \frac{\text{Serum Creatinine (}\mu\text{M/L)}}{88.4}$$

7.4.2. Hematology

Blood samples will be collected at Screening (Visit 1), Visit 3, and at the completion of the Double-Blind Fixed Dose Phase (Visit 6) or at the Early Termination Visit, if necessary, to assess hematology parameters, including: red blood cell count (RBC), hemoglobin (HGB), hematocrit (HCT), platelets, and white blood cell count (WBC) (with differential), neutrophils, lymphocytes, monocytes and eosinophils.

7.4.3. Clinical Chemistry

Blood samples will be collected at Screening (Visit 1), Visit 3, and at the completion of the Double-blind Fixed Dose Phase (Visit 7) or at the Early Termination Visit, if necessary, to assess clinical chemistries, including: total bilirubin, direct and indirect bilirubin, alkaline phosphatase (ALP), alanine aminotransferase (ALT/SGPT), aspartate aminotransferase (AST/SGOT), creatine phosphokinase (CPK) blood urea nitrogen (BUN), creatinine, glucose, total protein, albumin, total cholesterol, triglycerides, sodium, potassium, chloride and calcium. In addition, Endocrine panel (free T4 and TSH, IGF-1, and IGFBP-3) and Hepatitis serology (Anti-HAV IgM; S-HB Ag; S-HCV) will be assessed at Visit 1 only.

Approximate blood volumes to be obtained, per visit, are as follows, for children >5kg in weight*:

V1 Screening:	10.5 mL
V3:	4.5 mL
V4:	<2 mL (for CCI)
V6:	4.5 mL plus <1 mL (for CCI)
V7 EOS or ET:	4.5 mL plus optional <1 mL (for CCI)
Unscheduled visit:	12.3 mL maximum (all testing optional)
CCI:	<1 mL

* Blood sampling may be reduced for potential subjects who do not have the weight/blood volume capacity to undergo the protocol-specified blood collection requirements [for example <5 kg], as per local regulations and institutional guidelines. Prior to implementation of any reduction in blood sampling, the investigator is required to contact the Pfizer Study Clinician (via e-mail or phone) to discuss the applicability of a proposed reduced blood sampling plan. At a minimum, samples for chemistry and hematology will be collected at indicated visits.

7.4.4. Urinalysis

Urine samples will be collected at Screening (Visit 1), Visit 3, and completion of the Double-blind Fixed Dose Phase (Visit 6) or at the Early Termination Visit, if necessary, to assess the following: pH, specific gravity, colorimetric urine protein, glucose and ketones. Microscopic analysis will be performed only if the results of the urinalysis are abnormal and will include: red blood cells (RBCs), white blood cells (WBCs), casts, crystals, and bacteria. If it is not possible to collect a urine sample, despite appropriate efforts, the urine sample can

090177e18f46d803\Approved\Approved On: 31-Aug-2018 06:42 (GMT)

be omitted for that visit. The reason for lack of sample must be recorded and documented in source documentation.

7.5. Vital Signs, Height/Length and Weight

Blood pressure and pulse in the sitting or supine position are to be recorded at each visit as specified in the [STUDY PROCEDURES](#) section. Height/length will also be recorded at the Visit 1 and Visit 3, Weight will be recorded at Visits 1 and 3. Weight recorded at Visit 3 will be used to calculate the dosing assignment for all subsequent visits.

7.6. Physical and Neurological Examination

A physical examination will be performed and must be completed by a Medical Doctor (MD), Doctor of Osteopathy (DO), Nurse Practitioner (NP) or Physician Assistant (PA) or appropriate equivalent based upon normative country specific practices.

Full physical and neurological exams will be performed at Visit 1 and Visit 7 (ie, at the completion of the study or early termination). A brief physical exam and neurological exam documenting significant changes from the baseline exam will be performed at Visit 3.

Physical examinations will evaluate the following body systems/organs: general appearance; dermatological; head and eyes; ears, nose, mouth, and throat; pulmonary; cardiovascular; abdominal; genitourinary (optional); lymphatic; musculoskeletal/extremities; and neurological.

Any clinically significant changes from the entry examination will be recorded as adverse events and the specific finding(s) documented with an Investigator Comment.

Neurological exam will assess: level of consciousness, mental status, cranial nerve assessment, muscle strength and tone, reflexes, pin prick and vibratory sensation (the latter using a 128-Hz tuning fork), coordination and gait.

7.7. Electrocardiogram (ECG)

A 12-lead ECG will be performed at screening (Visit 1) and at the completion of the study (Visit 7). A central ECG reader will be used for this study. The following parameters will be assessed: PR interval, RR interval, QRS complex/duration, QT interval, QTc, and heart rate.

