The pharmacokinetics (PK), safety, and tolerability of pregabalin were evaluated in pediatric subjects 1 month to 16 years of age with partial onset seizures in the double-blind, placebo-controlled Phase 1 Study A0081074. Dose levels 2.5, 5.0, 10.0, and 15.0 mg/kg/day (given in equally divided doses twice daily) were administered for 8 days. Single and multiple dose PK were evaluated. Pregabalin peak concentration (C_{max}) and total exposure (area under the curve AUC) increased linearly with increasing dose (2.5, 5.0, 10.0 and 15.0 mg/kg/day) for each age group (1 month to 23 months, 2 to 6 years, 7 to 11 years, and 12 to 16 years). Pregabalin terminal $t_{1/2}$ averaged about 3 to 4 hours in pediatric subjects from 1 month to 6 years of age, and 4 to 6 hours in those 7 years of age and older. Pregabalin oral clearance normalized per body weight was 43% higher in the children with body weight less than 30 kg than in children whose body weight was 30 kg and higher. Apparent oral clearance of pregabalin was directly related to creatinine clearance. When dosed on a mg/kg/day basis, pregabalin daily exposure was approximately 30% lower in these subjects weighing less than 30 kg. The data from Study A0081074 has been used to define the dose range and frequency to be investigated in this study (Study A0081042) and additional Phase 3 efficacy and safety studies in the pediatric epilepsy population.

Pregabalin has been shown to be effective in the treatment of epilepsy in adults and is currently approved for the adjunctive treatment of POS in adults over a dose range of 150 to 600 mg/day (when taken 2 or 3 times a day). Thus, pregabalin's mechanism of action, being different from other anti-epileptic drugs, has the potential to expand treatment choices for children with epilepsy. This study is considered to have a positive risk benefit ratio for enrolling patients based on extensive previous experience with pregabalin in adults with POS and with the comprehensive safety screening and monitoring plans included in the present study design.

This study is one of several studies that will be conducted to assess the safety and efficacy of pregabalin in pediatric subjects with epilepsy and to address post approval commitments to US Food Drug Administration (FDA) and EU European Medicines Agency (EMA) regulatory authorities.

Complete information for pregabalin may be found in the Single Reference Safety Document which for this study is the Investigator Brochure.

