- Level 1: 7.0 mg/kg/day [6 mg/kg/day for subjects 1 to 3 months of age];
- Level 2: 14 mg/kg/day [12 mg/kg/day for subjects 1 to 3 months of age].

Subjects randomized to receive either Level 1 or Level 2 pregabalin will have a 5 day escalation phase, a 9 day fixed dose phase, and a 7 day taper phase. The taper phase should begin following the completion of the Double-Blind Fixed Dose Treatment Phase at Visit 6. Note: subjects who require early discontinuation should begin the taper period after the

decision is made to discontinue. Subject's daily dosing will be recorded by their parent(s)/guardian(s)/caregiver(s) as appropriate, in a daily dosing diary. Table 2 below summarizes dosing for the 3 double-blind treatments for the Escalation, Fixed-Dosing, and Taper Phases of the study. All active treatments will start at 3.5 mg/kg/day [3 mg/kg/day for subjects 1 to 3 months of age] and escalate to the final level as shown in Table 2, then taper back to 3.5 mg/kg/day [3 mg/kg/day for subjects 1 to 3 months of age] after the fixed dose phase.

Table 2. Double-Blind Dosing By Study Treatment, Study Phase

DOUBLE-BLIND PHASES						
Treatment ^a	Dose Escalation Phase		Fixed-Dose Phase		Taper Phase [*]	
	Age >3 months	Age ≤3 months	Age >3 months	Age ≤3 months	Age >3 months	Age ≤3 months
Placebo	Placebo	Placebo	Placebo	Placebo	Placebo	Placebo
Level 1:-	3.5 mg/kg/day x 5 days	3.0 mg/kg/day x 5 days	7.0 mg/kg/day x 9 days	6.0 mg/kg/day x 9 days	3.5 mg/kg/day x 7 days	3.0 mg/kg/day x 7 days
Level 2:	Step 1: 3.5 mg/kg/day x 2 days Step 2: 7.0 mg/kg/day x 3 days	Step 1: 3.0 mg/kg/day x 2 days Step 2: 6.0 mg/kg/day x 3 days	14 mg/kg/day X 9 days	12 mg/kg/day X 9 days	Step 1: 7.0 mg/kg/day x 4 days Step 2: 3.5 mg/kg/day x 3 days	Step 1: 6.0 mg/kg/day x 4 days Step 2: 3.0 mg/kg/day x 3 days

* Subjects who will not participate in Study A0081106 will discontinue study medication following the completion of the taper phase. For subjects who will enter Study A0081106, all subjects will initiate that study at a dose of 3.5 mg/kg/day [3 mg/kg/day for subjects 1 to 3 months of age] and may then escalate according to protocol requirements.

a Study drug will be administered TID in equally divided doses.

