6.2. Double-Blind Dose Escalation Phase

6.2.1. Visit 3 (Day 1 \pm 1) Randomization and Entry into Double-blind Dose Escalation Phase

Randomization: Subjects who satisfy all of the eligibility criteria at this study visit may be randomized and will receive the initial dose of study medication at the clinic during this visit.

The following activities will be performed at Visit 3:

- Verify conformance with entry criteria by reviewing inclusion/exclusion criteria.
- Verify the criteria for total number of qualifying seizures has been met by review of the Video-EEG by the investigator/or designee.
- Record all concomitant medications and non-drug treatments and procedures, including any ongoing AED's.
- Record weight and height/length.
- Assess and record adverse events.
- Perform brief physical examination which includes recording vital signs including blood pressure and pulse.

- Perform brief neurological examination.
- Collect blood and urine specimens for clinical laboratory assessments. If it is not feasible to obtain a urine sample, then no urine sample will be required.
- Assign randomization number and dispense blinded study medication via tele-randomization system.
- Train parent(s)/guardian(s)/caregiver(s) on study medication dosing and administration and demonstrate use of oral syringe/bottles. Have parent(s)/guardian(s)/caregiver(s) practice dosing in office to verify comprehension of dosing instructions.
- Administer first dose of study medication in clinic.
- Dispense daily dosing diary.
- Download Video-EEG recording data.
- Transmit Video-EEG data to central reader for assessment.
- Collect seizure event log and send to central reader.

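### ECGs and physical and neurological examinations are safety endpoints, but their only scheduled post-dose assessment is at the end of the taper, when neither active arm is on its assigned dose

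*Protocol*

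**What the plan says.** **Endpoints.** Protocol Section 2.2 and SAP Section 6.2 include the results of physical examinations, neurological examinations and ECGs in the evaluation of safety.

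**ECG.** Protocol Section 7.7: "A 12-lead ECG will be performed at screening (Visit 1) and at the completion of the study (Visit 7"). The Schedule of Activities and the visit lists in Sections 6.1 and 6.4.1 agree.

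**Examinations.** Protocol Section 7.6: "Full physical and neurological exams will be performed at Visit 1 and Visit 7 (ie, at the completion of the study or early termination"). It adds: "A brief physical exam and neurological exam documenting significant changes from the baseline exam will be performed at Visit 3". In the Visit 3 list (Section 6.2.1) that brief examination stands ahead of the entry "Administer first dose of study medication in clinic".

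**Visits 4, 5 and 6.** Sections 6.3.1, 6.3.3 and 6.3.4 contain no ECG and no physical or neurological examination.

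**Dosing.** Under Section 3.2, fixed dosing ends and the taper begins at Visit 6 (Day 15 ±2). Section 6.4 places the end of the taper at Visit 7 (Day 22 ±3). In Table 2, for children older than 3 months, Level 1 tapers at 3.5 mg/kg/day for 7 days, and the Level 2 entry is "Step 1: 7.0 mg/kg/day x 4 days Step 2: 3.5 mg/kg/day x 3 days".

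**Half-life.** Section 1.2 says that the terminal half-life "averaged about 3 to 4 hours in pediatric subjects from 1 month to 6 years of age".

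**The concern.** A safety endpoint informs on a dose only if it is measured while the child is on that dose, or soon enough afterwards for an effect to persist. Here the screening and Visit 3 assessments serve as baseline, and the next look comes once the dose has been stepped down. A reversible, exposure-related change in PR, QRS or QTc, or in consciousness, tone, coordination or gait, could be present throughout the 9 fixed-dose days and gone by Visit 7. The ECG and examination tables would then show little difference between either pregabalin arm and placebo. A reader of the report could take that as reassurance about 7 and 14 mg/kg/day, which the data cannot give.

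The examination matters here because Section 1.2 names dizziness (32%) and somnolence (22%) as the most common adverse effects in adults with partial onset seizures. Children under 4 are poorly placed to report such symptoms themselves.

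**Working it through.** **1. Reproduce the plan's own figure.** Escalation 5 + fixed dose 9 + taper 7 = 21 days, as Section 3 states.

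**2. Nominal dose by day** (Table 2, age over 3 months, mg/kg/day; taper starting on Day 15):

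| Day | Level 1 | Level 2 |
|---|---|---|
| 14 (last fixed-dose day) | 7.0 | 14.0 |
| 15 to 18 | 3.5 | 7.0 |
| 19 to 21 | 3.5 | 3.5 |
| 22 (Visit 7) | taper complete | taper complete |

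**3. Last taper dose as a share of the assigned dose.**
- Over 3 months: 3.5/7 = 50% (Level 1); 3.5/14 = 25% (Level 2).
- 3 months or younger: 3/6 = 50%; 3/12 = 25%.
- Difference between Level 2 and Level 1 at the last taper step: 3.5 − 3.5 = 0, or 3 − 3 = 0.

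**4. Visit windows.** Visit 6 may fall on Days 13 to 17 (5 days) and Visit 7 on Days 19 to 25 (7 days), which gives 5 × 7 = 35 combinations. I assume that the taper starts on the day of Visit 6 and count whole days. Age over 3 months:

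| Visit 6 day | Level 2 on 7.0, Level 1 on 3.5 | Both on 3.5 | Taper complete in both |
|---|---|---|---|
| 13 | 0 | 1 | 6 |
| 14 | 0 | 2 | 5 |
| 15 | 0 | 3 | 4 |
| 16 | 1 | 3 | 3 |
| 17 | 2 | 3 | 2 |
| Total | 3 | 12 | 20 |

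Both active arms are at the same nominal level in 12 + 20 = 32 of 35. The other three are Visit 6 on Day 16 with Visit 7 on Day 19, and Visit 6 on Day 17 with Visit 7 on Day 19 or 20. In those, Level 2 is at 7.0/14 = 50% of its assigned dose. No combination gives 7.0 in Level 1 or 14.0 in Level 2. These are counts of possible combinations, not predicted frequencies.

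**5. Carry-over.** The fraction of a drug level left after t hours is 0.5^(t/half-life). After 24 h it is 0.5^(24/3) = 0.4% to 0.5^(24/4) = 1.6%. Nothing material from the fixed-dose phase can remain a week later.

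**6. Visit 3.** Even if the brief examination were done after the first dose, that dose is the escalation dose (3.5 or 3 mg/kg/day). It could not supply an assigned-dose observation.

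**The case against.** The other side has several good points.

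- **No dose-specific commitment for these endpoints.** A reader might infer one from the words "relationship to study drug and dosing level" in Section 7.3. They sit inside the parenthesis that describes adverse event data; ECGs and examinations come after it. The safety objective in Section 2.1 concerns pregabalin generally, and two dose levels are named only in the primary efficacy objective. It would be too strong to say that the safety objective goes unanswered.
- **No formal comparison is spoiled.** SAP Section 8.2.3 plans no inferential safety analysis, and protocol Section 9.4 puts ECGs and examinations in listings and summary tables. The risk is one of interpretation.
- **Other on-dose safety data exist.** Adverse events are collected throughout. Vital signs are taken at Visits 5 and 6, and at Visit 4 on the border between escalation and fixed dosing. Laboratory samples are drawn at Visit 6. Visit 5 is an inpatient stay of up to 72 hours of recording on fixed dose. Clinically evident changes can be reported as adverse events. These sources do not supply centrally read intervals or a structured examination.
- **Exceptions.** Section 6.5 lets a child stop early without taper, with Visit 6 and 7 assessments done as possible, so a few children could be examined near the assigned dose. They are unplanned and selected by withdrawal, and give no randomised comparison.
- **Visit 7 may be a deliberate end-of-study check.** The ECG and examination timing is consistent across the protocol, and Section 8.3 counts drug withdrawal effects as possible adverse events. A post-taper look has its own use.

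A reader might also see the phrase "at the completion of the Double-blind Fixed Dose Phase (Visit 7") in Section 7.4.3 as the same fault. It is a separate labelling error: blood is drawn at both Visits 6 and 7, so no data are lost. Nor do the documents support a percentage for residual exposure at Visit 7, because they do not give the interval from the last taper dose to the assessment.

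The scheduling fact survives all of these points.

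**Conclusion.** The point holds for ECGs and physical and neurological examinations, and for these only. For children who follow the schedule, these named endpoints are never observed at either assigned dose: 0 of 35 window combinations. At the nominal Visit 7 the two active arms are no longer separated by dose. A null summary against placebo would describe the post-taper state and would say nothing about Level 1 or Level 2.

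This rests on Table 2 and the visit windows as written, with the taper starting on the day of Visit 6. The half-life supports the conclusion, but the 50% and 25% ratios do not depend on it. Efficacy is unaffected. This is a worthwhile and inexpensive improvement, not a flaw that undermines the trial.

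**What to change.** **Preferred.** Move the post-dose 12-lead ECG and the full physical and neurological examination from Visit 7 to Visit 6, before the first taper dose, and keep a brief examination at Visit 7. The places to edit are the Schedule of Activities and protocol Sections 6.3.4, 6.4.1, 7.6 and 7.7. In SAP Section 8.2.3, name Visit 6 as the on-treatment time point for ECG and examination summaries.

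**Cost.** No assessment is added except the brief Visit 7 examination, and no dosing rule changes. Visit 6 is already attended, with vital signs and laboratory samples. There are two downsides:
- There would be no routine post-taper ECG.
- A mid-study change mixes time points. The blinded re-estimation was set for when about two thirds of 123, or 82 children, could have completed, and it has been done. At most roughly 150 − 82 = 68 would come under the new schedule, so results must be summarised by visit.

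**If the schedule stays.** State in the SAP and the report that ECG and examination results describe the post-taper state and do not support safety conclusions at the assigned doses.

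**Separately.** Reconcile the Visit 7 label in Section 7.4.3 with Sections 7.4.2 and 7.4.4 and the Schedule of Activities, which tie the end of fixed dosing to Visit 6.
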